9. TREATMENTS

9.1. Investigational Drug Product

Eteplirsen injection is intended for IV infusion.

9.2. Packaging and Labeling

Eteplirsen injection will be supplied as a sterile, isotonic, clear, colorless phosphate buffered saline solution with no preservatives at a concentration of 50 mg/mL in single-use vials containing a nominal volume of 2 mL or 10 mL.

The label text for the IP will comply with current Good Manufacturing Practice (cGMP) and other applicable regulatory requirements, and will minimally include the contents of the vial, the appropriate cautionary statements per 21 Code of Federal Regulations (CFR) 312.6, lot number (or alternative code), storage conditions, and the name of the Sponsor.

9.2.1. Receipt of Investigational Product

A proof of receipt, which details the quantity and description of the IP, will accompany the shipment from the Sponsor or designee to the Investigator. Details for IP receipt, storage, and dispensation recordkeeping are located in the study specific Pharmacy Manual. The Investigator must ensure that the IP is maintained in a controlled location, with limited access and temperature monitoring under appropriate storage conditions.

9.2.2. Storage

Vials of IP must be stored at a consistent temperature from 2°C to 8°C in a secured, limited-access area with temperature recording, controls, and monitoring. Details for preparation of the diluted IP for administration can be found in the study specific Pharmacy Manual.

9.3. Treatments Administered

Eligible patients who have an out-of-frame deletion that may be treated by skipping exon 51 will receive 30 mg/kg/week eteplirsen as an IV infusion for up to 96 weeks (treated group). Eligible patients who have out-of-frame deletions that are not amenable to treatment by skipping exon 51 will remain on their existing standard of care but will not receive eteplirsen throughout the study (untreated control group).

For the treated group, the following guidelines for the timing of dosing should be followed throughout the study:

1. Patients should receive eteplirsen once every 7 days starting on Study Day 1. A window of ±3 days from the scheduled dose is acceptable after the first infusion. For visits where safety assessments are not being collected, optional in-home administration of eteplirsen by a visiting nurse may be available after Week 25. For in-home dosing, additional instructions will be provided in a separate manual to the visiting nurse.

- 2. Patients may not receive 2 separate doses of eteplirsen within the same 60-hour period.
- 3. The medical monitor should be contacted in the event of a missed dose.

9.3.1. Disposition of Unused Investigational Drug Product

All unused IP vials must be maintained under adequate storage conditions in a limited-access area until time of use. Upon completion of the study, any remaining unused IP vials will be returned to the Sponsor or destroyed per the site-specific standard operating procedures to minimize the potential for contamination. Final drug accountability will be monitored by the Sponsor or its representative.

9.3.2. Administration of the Investigational Product

The dose of eteplirsen will be calculated based on the most recent patient weight obtained at the site prior to the current visit. Eteplirsen should be prepared for dosing by following the steps detailed in the study specific Pharmacy Manual.

Eteplirsen will be administered as an IV infusion over a period of approximately 35 to 60 minutes. It is recommended that a topical anesthetic cream (e.g., lidocaine 2.5%, prilocaine 2.5%, or LMX4 cream) be applied to the infusion site prior to each administration of eteplirsen.

An implanted venous access port may be inserted for eteplirsen administration at the discretion of the Investigator. If eteplirsen is administered into an existing IV line, the line should be flushed with normal saline before and after administration of eteplirsen. After eteplirsen administration and the saline flush, the port may be flushed with heparin to heplock the port prior to removal of the infusion line.

No other medications may be administered concomitantly during the eteplirsen infusion.

All treated patients will be observed for at least 1 hour following the end of each eteplirsen infusion.

9.4. Dosing Considerations

9.4.1. Dose Modification, Reduction, or Delay

There is no provision for dose alteration in this study. If a patient experiences an AE that requires interruption of administration of eteplirsen for ≥ 2 doses, the Investigator will consult with the Medical Monitor to determine whether the patient may resume treatment.

9.4.2. Treatment Discontinuation

The Investigator or study staff will document the reason(s) for treatment discontinuation on the case report form (CRF). The following may be justifiable reasons for the Investigator or Sponsor to discontinue a patient from treatment:

• The patient was erroneously included in the study (i.e. was found to not have met the eligibility criteria).

- The patient experiences an intolerable or unacceptable AE.
- The patient is unable to comply with the requirements of the protocol.
- The patient participates in another investigational study that would interfere with the assessments in Study 4658-301.

Patients who receive at least one (1) dose of IP and who are withdrawn from treatment within 4 weeks after a Functional Assessment visit (Week 12, 24, 36, 48, or 72) will be asked to return for an End of Study visit (to complete the Week 148 assessments) within 4 weeks from their last infusion. Patients who receive at least one (1) dose of IP who are withdrawn from treatment more than 4 weeks after a Functional Assessment visit (Week 12, 24, 36, 48, or 72) will be asked to complete all Early Termination (Week 96) assessments as soon as possible after withdrawal and to complete an End of Study visit (to complete the Week 148 assessments) within 4 weeks after their last infusion. Patients who withdraw during the Safety Extension Period (Weeks 97-148) in order to transition onto commercial drug do not need to complete the End of Study visit assessments.

9.5. Method of Assigning Patients to Treatment

Enrolled patients who have an out-of-frame deletion that may be treated by exon 51 skipping (e.g., deletions of exons 45-50, 47-50, 48-50, 49-50, 50, 52, 52-63) will be assigned to the treated group and will receive eteplirsen 30 mg/kg/week.

Enrolled patients who have an out-of-frame deletion that is not amenable to treatment by exon 51 skipping but is amenable to treatment by skipping other exons (i.e., whole exon deletions in which the reading frame may be restored by skipping 1 or 2 exons) will be assigned to the untreated control group.

9.6. Blinding and Randomization

This is an open-label study, and therefore patients and Investigators will be aware of the patient's treatment. However, to minimize assessment bias, every effort will be made to keep the clinical evaluators unaware of the treatment group of the patients, and all biological efficacy endpoint evaluations will be performed by blinded assessors.

9.6.1. Maintaining the Blind for Clinical Evaluators

Clinical evaluators will be instructed on how to maintain blinding to treatment group as well as possible through training. Specifically, the clinical evaluators will:

- Not be involved in any aspect of care for the patients over the course of the study and will not have access to any clinical patient records including laboratory values, genetic analyses, or study-specific assessment and treatment schedules.
- Not have contact with the parents or caregivers of the patients.
- Avoid conversation with the patients about treatment, other assessments including muscle biopsies, and any other disease related topics.

 Strive to keep the conversation with patients to the necessary minimum to allow for optimal clinical assessments while keeping the topic relevant to the current evaluation.

Patients will be requested not to discuss their study treatment with the clinical evaluators.

In order to maintain the study blind, interaction between parents and clinical evaluators will be minimized. Parents of study participants will therefore be requested not to interact with clinical evaluators and will be asked to not publicly discuss their child's participation in this study. It will also be explained to parents that they will not receive any information on the clinical efficacy evaluation until the study is complete.

9.6.2. Laboratory Assessments

All laboratory assessments, notably IHC, and Western blot assays will be performed so that the raters are unaware of the time point at which the sample has been taken. A detailed description of these procedures can be found in the Laboratory Manual.

9.6.3. Randomization for Muscle Biopsy Schedule (Treated Group Only)

Upon qualification for the study during the Baseline visit, patients in the treated group will undergo muscle biopsy, and will be randomized to a second muscle biopsy schedule at Week 24 (20%), Week 48 (40%), Week 72 (20%), or Week 96 (20%). Patients in the untreated control group will not undergo muscle biopsy at any time point.

9.7. Prior and Concomitant Medications and Therapeutic Procedures

For both treatment groups, the dosing regimen for oral corticosteroids for treatment of DMD including, but not limited to, prednisolone, prednisone, or deflazacort, should be kept the same throughout the study except for modifications to accommodate changes in weight.

For both treatment groups, the following therapies may be used before enrollment and throughout the study; however, the dosage should be constant throughout the treatment period, unless clinically indicated:

- Oral ACE inhibitors, including but not limited to perindopril and lisinopril
- Oral β-blockers, including but not limited to carvedilol and atenolol
- Angiotensin-receptor blockers, including but not limited to losartan, irbesartan, valsartan, and candesartan
- Oral laxatives, including but not limited to lactulose, Senokot, and Movicol
- Vitamin D and calcium supplements
- Alendronate (Fosamax) or other bisphosphonates used to treat osteoporosis/osteopenia by inhibiting osteoclasts

• Over-the-counter herbal preparations, including herbal supplements, vitamins, minerals, and homeopathic preparations, provided the patient had been on stable doses for 24 weeks before enrollment in this study

Recommendations for selection of medications and interventions during anesthesia include:

- The use of depolarizing muscle relaxants such as succinylcholine are not permitted in any case due to their potential to induce rhabdomyolysis in patients with DMD
- Volatile anesthetics should be avoided if possible, also due to a risk of rhabdomyolysis

Other concomitant medications (e.g., vitamins or other non-RNA antisense medications) may also be taken if, in the opinion of the Investigator, they do not interfere with study assessments and outcomes. Every attempt should be made to keep the dosage constant throughout the study treatment period (i.e., through Week 96).

Introduction of new physiotherapy interventions during the course of the study must be avoided unless the best interests of the patient are at risk. Should a contracture develop during the course of the study, and it is considered in the best interest of the patient to treat the contracture, then any of the following interventions may be used to reduce the contracture, but they must be clearly documented:

- Contracture control devices
- Night splints
- Stretching exercises (passive, active, self)
- Serial casting

The following therapies are **not permitted** during the conduct of this study:

- Systemic or oral steroids for non-DMD conditions, except for treatment of an acute condition (e.g., poison ivy)
- Investigational agents for the treatment of DMD
- Any medication with the potential to affect muscle mass, strength, and/or function, such as, but not limited to, growth hormone and phosphodiesterase type 5 inhibitors
- Immunosuppressants (other than oral or systemic corticosteroids)
- Aminoglycoside antibiotic or statin (unless discussed and agreed upon with the Investigator and Medical Monitor)

9.8. Treatment Compliance

Treatment compliance will be assessed via compliance with scheduled weekly infusions.

10. STUDY ASSESSMENTS

10.1. Study Schedule of Events

Schedules outlining the study assessments and times of assessments are shown in Section 2. Written informed consent from the parent/legal guardian(s) and assent from the patient (if applicable) to participate in this study must be obtained prior to beginning any of the procedures for Study 4658-301 (see Section 14.3 for further details).

10.2. Study Assessments by Visit

Assessments of AEs and concomitant medications will be performed at every study visit. Various study assessments may be performed at different sites.

A 'Local Site' will be the site a patient most frequently visits for infusions and routine assessments. All assessments scheduled on the same day as eteplirsen administration are to be completed prior to initiation of eteplirsen infusion, except for postdose blood draws for PK as indicated in Section 2.

A 'Hub Site' will perform functional efficacy and cardiac assessments. Patients enrolled at certain Local Sites will therefore need to travel to a Hub Site. A Hub Site may also be a particular patient's Local Site. Hub Sites have been introduced to minimize the number of clinical evaluators and thereby reduce rater-dependent variability in the study cohort. Each Hub Site will have at least 2 expert clinical evaluators who will have undergone standardized training and have been certified to be capable of performing all clinical assessments as specified for this study. To further reduce variability, every effort should be made to have each patient assessed by the same clinical evaluator for each specific assessment throughout the entire study; all assessments will be done in the same order as listed in the Clinical Evaluator Manual, at approximately the same time of day, and clinical evaluators will not have access to prior test results or information related to study-specific or routine patient care. Efficacy evaluations will be performed in the morning and cardiac assessments will be performed after completion of the functional assessments, at a consistent time of day for each visit during the course of the study.

To reduce the burden on the untreated control patients, all protocol-specified assessments after Week 12 may be performed at the Hub Site (Table 5). If a patient transfers to their assigned Hub Site for collection of safety assessments (e.g., laboratory assessments, vital signs, and physical examinations), the functional assessments must be done first, and the safety assessments should be done after completion of the functional assessments.

A 'Surgical Unit' will perform study-specific muscle biopsy procedures. Muscle biopsies for all treated patients will be performed at only 2 surgical sites, and all muscle biopsy tissue preparation including sectioning will be performed at a single central pathology laboratory according to a predefined protocol to reduce potential bias. Patients enrolled at certain Local Sites will need to travel to one of the 2 surgical sites for the biopsy procedures. A Surgical Unit may also be a particular patient's Local and/or Hub Site. However, personnel performing 'Hub'

and 'Surgical' functions will be clearly separated from those performing 'Local' functions and will not have access to any information related to routine care or treatment of the patient.

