a Patients may continue in the safety extension for up to 48 weeks, until the product is commercially available or until they can transition into a separate eteplirsen study.

b Early termination assessments are the same as Week 144 assessments.

c Full physical examination: general appearance, head, eyes, ears, nose, and throat (HEENT), heart, chest, abdomen, skin, lymph nodes, extremities, musculoskeletal, and neurological systems.

d Vital signs include blood pressure, heart rate, respiration, and oral temperature. On infusion days, vital signs will be measured prior to infusion and approximately 5 and 30 minutes after the end of the infusion. If the patient has not experienced an infusion reaction after the first year of treatment, vital signs may be reduced to pre-infusion and 30 minutes after the end of the infusion.

Table 5: Schedule of Events for Untreated Control Patients - Screening Through End of Study

Assessments	Up to	10 weeks	prior to Week 1ª				Olara		•. ah			
Study Period		ening p to -3w	Baseline -4w to Day -1&-2		(2-da	ay HS visi		rvation Po t Weeks 1		48, 72, an	nd 96)	
Week	1-day visit	2-day visit	2-day visit (3-5w after Screening at HS)	W1°	W4	W8	W12	W24	W36	W48	W72	W96/ ET ^b
Informed consent for screening at local site	X											
Informed consent for screening at HS (if different from local site)		HS										
Informed consent to participate as a control patient (no consent form needed at W12 if local is same as HS)				X			HS					
Assess inclusion/exclusion criteria	X	HS	HS									
Confirm eligibility ^d			X	X								
Medical history	X											
Full physical examination ^e	X			X	X		X	X	X	X	X	X
Brief physical examination ^e						X						
Vital signs ^f	X		HS	X	X	X	X	X	X	X	X	X
Weight	X			X	X	X	X	X	X	X	X	X
Safety laboratory assessments ^g	X ^h			$X^{h,i}$	X	X	X	X	X	X	X	X

Table 5: Schedule of Events for Untreated Control Patients - Screening Through End of Study, continued

Assessments	Up to	10 weeks	prior to Week 1ª				Ohga	rvation P	out o db				
Study Period		ening p to -3w	Baseline -4w to Day -1&-2		(2-da	ny HS visi	ts occur a			48, 72, an	d 96)		
Week	1-day visit	2-day visit	2-day visit (3-5w after Screening at HS)	W1°	W4	W8	W12	W24	W36	W48	W72	W96/ ET ^b	
Immunogenicity				Xi	X	X	X	X	X	X	X	X	
CCI													
Whole blood for DMD genotyping	X												
CCI													
Height (and ulnar length at HS visits)	X		HS				HS	HS	HS	HS	HS	HS	
6MWT ^j		HS	HS				HS	HS	HS	HS	HS	HS	
NSAA ^j			HS				HS	HS	HS	HS	HS	HS	
CCI													

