ECG ¹		HS	HS				HS	HS	HS	HS	HS	HS	
ECHO ¹		HS						HS		HS	HS	HS	
Conmed/therapy	Continuous												
AE assessment					Со	ontinuous							

Table 5: Schedule of Events for Untreated Control Patients - Screening Through End of Study, continued

Assessments		Up to	10 weeks	prior to Week 1ª		Observation Period ^b							
	Study Period		ening o to -3w	Baseline -4w to Day -1&-2		(2-da	y HS visi				48, 72, an	d 96)	
	Week	1-day visit	2-day visit	2-day visit (3-5w after Screening at HS)	W1°	W4	W8	W12	W24	W36	W48	W72	W96/ ET ^b

X = Local Site, HS = Hub Site

Functional assessments at Hub Sites beyond Week 1 have a ±2 week window.

Note: To reduce the burden on the untreated control patients, all protocol-specified assessments after Week 12 may be performed at the Hub Site. If a patient transfers to their assigned Hub Site for collection of safety assessments (e.g., laboratory assessments, vital signs, and physical examinations), the functional assessments must be done first, and the safety assessments should be done after completion of the functional assessments.

- a Not including the time needed for genotyping if the patient has not previously been genotyped. If the patient has not been previously genotyped, then no other screening procedures other than informed consent and genotyping may be done until results of genotyping are known, at which time the 10-week Screening period will begin.
- b Early termination assessments are the same as Week 96 assessments. An Early Termination visit is required if the patient discontinues more than 4 weeks after a Functional Assessment visit (Week 12, 24, 36, 48, or 72).
- c Week 1 should occur within 4 weeks of the Baseline Functional Assessment visit (performed at the Hub Site). If the Week 1 visit is more than 4 weeks after Baseline, the patient is required to repeat the Baseline functional assessments. The repeated 6MWT assessment must be within 15% of the previous Baseline assessment in order to meet eligibility.
- d Eligibility will be assessed during Screening and confirmed by the local site after completion of the 6MWT at the Baseline visit. Eligibility will be reconfirmed at Week 1 based on all available data including safety laboratory assessments.

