10.2.3. Weekly Infusions (Weeks 1-96) (for the treated group only)

At Local Sites:

- Vital signs, including include blood pressure, heart rate, respiration, and oral temperature. Vital signs will be measured 30 minutes prior to the start of the infusion and 5, 30, and 60 minutes after the end of the infusion. If the patient has not experienced an infusion reaction after the first year of treatment, vital signs may be reduced to pre-infusion and 30 minutes after the end of the infusion. Vital signs should be collected as close to or at the exact indicated times as possible.
- Eteplirsen will be administered via an IV infusion. Patients should be closely monitored for at least 1 hour following the completion of all infusions. It is recommended that a topical anesthetic cream (e.g., lidocaine 2.5%, prilocaine 2.5% or LMX4 cream) be applied prior to infusions. Refer to the Pharmacy Manual for specific instructions regarding IP reconstitution with normal saline.

10.2.4. Additional Procedures for Week 1

The assessments below should occur during a single day at a patient's Local Site.

- Full physical examination, including examination of general appearance, HEENT, heart, chest, abdomen, skin, lymph nodes, extremities, musculoskeletal, and neurological systems
- Vital signs
- Weight (This measurement will be used to calculate the eteplirsen dose for patients in the treated group.)
- Safety laboratory assessments, including chemistry, hematology, coagulation, and urinalysis
- Immunogenicity
- At a subset of sites for patients in the treated group, 1 blood sample for assessing plasma drug concentrations (PK) will be taken within 2 hours prior to the start of the first infusion of eteplirsen.

10.2.5. Additional Procedures for Week 4

Assessments should occur during a single day at the patient's Local Site.

- Full physical examination, including examination of general appearance, HEENT, heart, chest, abdomen, skin, lymph nodes, extremities, musculoskeletal, and neurological systems
- Vital signs
- Weight
- Safety laboratory assessments, including chemistry, hematology, coagulation, and urinalysis
- Immunogenicity

10.2.6. Additional Procedures for Week 8

Assessments should occur during a single day at the patient's Local Site.

- Brief physical examination, including examination of general appearance, HEENT, heart, chest, abdomen, and skin
- Vital signs

- Weight
- Safety laboratory assessments, including chemistry, hematology, coagulation, and urinalysis

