• Depending upon randomization, patients in the treated group may have a muscle biopsy performed following the Week 24, 48, 72, or 96 (Section 10.2.10 for Week 96 procedures) infusion and functional assessments. The biopsies must occur within 2 weeks after the specified visit, after the clinical evaluation, and at least 48 hours after the most recent infusion.

10.2.8. Additional Procedures for Weeks 16, 32, 40, 44, 60, 84 (for the treated group only)

At Local Sites:

• Brief physical examination, including examination of general appearance, HEENT, heart, chest, abdomen, and skin

- Vital signs
- Weight
- At Week 16 and Week 32: At a subset of sites for patients in the treated group, blood samples for assessing plasma drug concentrations (PK) will be obtained 5 to 10 minutes after completion of drug administration.
- At Week 40, Week 60, and Week 84: At a subset of sites for patients in the treated group, PK blood samples will be obtained within 2 hours prior to the start of the infusion and 5 to 10 minutes after completion of the infusion. PK samples will also be taken approximately 1-2 hours and 2-4 hours after completion of drug administration.
- **10.2.9.** Additional Procedures for Weeks 20, 28, 44, 52, 56, 64, 68, 76, 80, 88, 92 (for the treated group only)

At Local Sites:

- Brief physical examination, including examination of general appearance, HEENT, heart, chest, abdomen, and skin
- Vital signs
- Weight
- 10.2.10. Additional Procedures for Week 96 (or Early Termination Visit, if more than 4 weeks after a Functional Assessment Visit)

At Local Sites:

- Full physical examination, including examination of general appearance, HEENT, heart, chest, abdomen, skin, lymph nodes, extremities, musculoskeletal, and neurological systems
- Vital signs
- Weight
- Safety laboratory assessments, including chemistry, hematology, coagulation, and urinalysis
- Immunogenicity
- At a subset of sites for patients in the treated group, blood samples for assessing plasma drug concentrations (PK) will be obtained within 2 hours prior to the start of the infusion, at the end of the infusion prior to flushing the infusion line, and 5 to 10 minutes after completion of the infusion. PK samples will also be taken approximately 1-2 hours and 2-4 hours after completion of drug administration.

At Hub Sites:

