7.9.1 Adverse Events

Adverse events will be coded using Medical Dictionary for Regulatory Activities (MedDRA Version 17.1 or higher). This coding system provides five levels to classify AEs. In general, AEs will be presented by system organ class (SOC) and PT but other classifications may be used if warranted.

The sorting order for the AE incidence tables, unless otherwise specified, will be by decreasing frequency in the active treatment arm. Multiple occurrences of the same AE (at the PT level) in the same patient will be counted only once in the frequency tables. If a patient experiences multiple episodes of the same event with different relationship/severity, the event with the strongest relationship or maximum severity to investigational drug product will be used to summarize AEs by relationship and severity. For example, for the table of AEs by SOC and PTs sorted by decreasing frequency presented by treatment group, SOC will be presented in decreasing frequency order of the active treatment column, and within each SOC, PTs will be presented in decreasing order of active treatment column. A patient is counted only once within each SOC and PT.

If a patient experiences multiple events that map to a single PT, the maximal severity grade and strongest investigator assessment of relation to study medication will be assigned to the PT for the appropriate summaries. Should an event have a missing severity or relationship, it will be classified as having a severity of “SEVERE” and/or a “DEFINITELY RELATED” relationship to study medication.

An overall summary of AEs table will be presented which will include:

- Number of Treatment-emergent AEs (TEAEs)
- Number of TEAEs by Severity
- Number of patients with at least 1 TEAE
- Number of patients with at least 1 Severe TEAE
- Number of patients with at least 1 treatment-related TEAE
- Number of patients with at least 1 treatment-emergent SAE
- Number of patients with at least 1 treatment-related, treatment-emergent SAE
- Number of patients with at least 1 TEAE leading to discontinuation of study drug
- Number of patients with a TEAE leading to death

Treatment-Emergent AEs (TEAEs)

The following TEAEs summary tables will be presented by treatment group:

- TEAEs by SOC and PT
- TEAEs by SOC, PT, and severity

- TEAEs by descending frequency of PT
- Treatment-related TEAEs by SOC and PT
- Treatment-related TEAEs by SOC, PT, and severity
- Treatment-related TEAEs by descending frequency of PT

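### AEs are asked about weekly in treated boys but up to 24 weeks apart in controls, so the by-arm TEAE tables are likely to overstate the treated-minus-control contrast for short-lived, non-serious events

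*Protocol*

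**What the plan says.** Protocol 10.2 links AE collection to attendance: "Assessments of AEs and concomitant medications will be performed at every study visit".

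**Treated arm.** Protocol 9.3 sets the rhythm: "Patients should receive eteplirsen once every 7 days starting on Study Day 1". Protocol 10.2.3 carries weekly infusions to Week 96 for this arm only. After Week 25, some infusions may be given at home by a visiting nurse, at visits without safety assessments (Protocol 7.1 and 9.3).

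**Control arm.** Protocol Table 5 ("Schedule of Events for Untreated Control Patients - Screening Through End of Study") lists Weeks 1, 4, 8, 12, 24, 36, 48, 72 and 96. The intermediate visits are confined to the treated arm, as the heading of Protocol 10.2.9 shows: "Additional Procedures for Weeks 20, 28, 44, 52, 56, 64, 68, 76, 80, 88, 92 (for the treated group only)". Neither document schedules a telephone call, diary or other contact for controls between visits. The Table 5 footnote adds slack: "Functional assessments at Hub Sites beyond Week 1 have a ±2 week window".

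**Collection period.** The AE row is marked as continuous in the schedules of both arms, and Protocol 11.1 requires every AE from consent onward to be recorded.

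**Analysis.** SAP 7.9.1 states: "The following TEAEs summary tables will be presented by treatment group". One listed table keeps TEAEs that occur in at least 2% of the active arm and more often than in the untreated arm. SAP 7.9 describes the safety analyses as descriptive. Nothing in SAP 7.9.1 allows for the difference in contact frequency.

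**The concern.** A headache, a bout of vomiting or a minor fall is easily reported to someone who asks within days. After three or five months it may well be forgotten. If the two arms are asked at very different intervals, the treated arm can show more minor AEs even when the drug causes none.

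This is separate from unequal length of follow-up. Cutting both arms at Week 96 leaves it in place. So does a person-time rate, because the missing events are in the numerator while the control person-time is counted in full.

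The part of the plan most exposed is the 2% table, because an AE enters it only by exceeding the control percentage. Differential recording therefore affects which events are listed as more frequent on drug.

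**Working it through.** The plan states no figure on this point, so there is none to reproduce.

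**1. Contact schedule (from the protocol).** Counting from the start of treatment or observation, the control gaps are 4, 4, 4, 12, 12, 12, 24 and 24 weeks, total 96. Treated gaps are 1 week throughout. With the ±2-week windows, a 24-week control gap can reach 28 weeks.

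**2. Control time far from the next enquiry (no recall assumption).**
- More than 4 weeks before the next visit: sum of (gap − 4) = 3×0 + 3×8 + 2×20 = 64 weeks; 64/96 = 67%. Treated: 0%.
- Mean wait to the next enquiry: sum of (gap²/2)/96 = (3×8 + 3×72 + 2×288)/96 = 816/96 = 8.5 weeks. Treated: 0.5 week.
- Taking Week 1 to Week 4 as 3 weeks (total 95) gives 64/95 = 67% and 8.6 weeks.

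**3. Share of resolved minor AEs recorded (recall assumed).** Suppose the chance of recall halves every *h* weeks, with k = ln 2/*h*. The share recorded is sum of [(1 − exp(−k·gap))/k]/96. With equal true rates in both arms:

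| h (weeks) | Treated | Control | Event-rate ratio |
|---|---|---|---|
| 4 | 0.918 | 0.366 | 2.51 |
| 8 | 0.958 | 0.549 | 1.74 |
| 12 | 0.972 | 0.653 | 1.49 |
| 26 | 0.987 | 0.809 | 1.22 |
| 52 | 0.993 | 0.896 | 1.11 |
| perfect recall | 1 | 1 | 1.00 |

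**4. Patient-level scale.** Most SAP tables count a patient once per preferred term. With Poisson events and true incidence p in both arms, recorded incidence is 1 − (1 − p)^share. For p = 50%, recorded incidence is 47% v 22% (h = 4; ratio 2.1), 49% v 32% (h = 8; 1.5), 49% v 36% (h = 12; 1.35), 50% v 43% (h = 26; 1.15) and 50% v 46% (h = 52; 1.08). For p = 80%, the ratios at h = 4, 8 and 12 are 1.7, 1.3 and 1.2. The more common the AE, the smaller the patient-level distortion.

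**5. The 2% table.** Exact binomial sums were run for the planned 80 treated (70 + 10) and 30 controls (20 + 10). An AE with true incidence 20% in both arms enters the table 50% of the time when recording is equal. That rises to 94%, 85% or 65% at h = 4, 8 or 26.

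**6. Sensitivity to home infusion.** If every treated boy were asked only at 4-weekly site visits after Week 25, the treated shares at h = 4, 8 and 12 would be 0.774, 0.876 and 0.914. The ratios would then be 2.1, 1.6 and 1.4.

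**7. Effect of a 28-day common window.** Controls would wait at most 4 weeks: share (1 − exp(−4k))/(4k) = 0.721, 0.845, 0.893 at h = 4, 8, 12. Treated boys are still asked weekly (0.918, 0.958, 0.972). Residual ratios are 1.27, 1.13 and 1.09. The window uses 8×4 = 32 of 96 weeks.

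**The case against.** **All AEs must be recorded in both arms.** The AE rows are marked continuous and Protocol 11.1 places the duty on sites throughout. This is why under-recording is likely and not certain. It fixes the collection period, however, and does not equalise how often anyone asks.

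**The size is assumed.** This stands. No recall rate appears in either document, and the ratio is 1.0 with perfect recall. A reader might take 2.5 as the expected distortion; the documents do not support any single value. It is also an event-level figure, and most of the tables count patients.

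**The SAP disclaims comparison.** SAP 6.3, 7.8 and 8.1 say that the arms will not be compared, citing the small control group, its dropout and population differences. SAP 7.9 calls safety descriptive. This rules out formal inference. It does not remove the 2% table, whose entry rule is itself a contrast with controls.

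**Treated enquiry may not be weekly throughout.** Home infusions are allowed where safety assessments are not collected, and Protocol 10.4 lists AE collection among the safety parameters. Protocol 10.2 says every visit, so the text is ambiguous. Step 6 shows that the gap narrows but remains.

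**The schedule reflects weekly IV treatment against an untreated arm.** This is fair, and the proposed change leaves the visits alone.

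**Conclusion.** The point holds as a likely bias in the between-arm contrast for short-lived, non-serious AEs. The asymmetry comes directly from the schedules: 67% of control follow-up against 0% of treated follow-up lies more than 4 weeks before the next scheduled enquiry. The treated figure assumes that AEs are asked about at every infusion, including those at home. The direction follows if recall is imperfect and decays similarly in both arms. The size does not come from the documents: the assumed range runs from about 2.5 down to 1.1, and to 1.0 with perfect recall, with smaller patient-level ratios for common AEs.

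Two stronger readings are tempting and are not supported. One is that the treated arm's AE rates are inflated; what is likely to be overstated is the difference from controls, and the treated rates themselves are little affected. The other is that the controls are useless as a safety reference; SAEs and long-lasting AEs should be little affected by the asking interval.

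**What to change.** Add to SAP 7.9.1 one supplementary TEAE table by arm, through Week 96. Count only AEs with onset in the 28 days before each visit scheduled in both arms (Weeks 4, 8, 12, 24, 36, 48, 72 and 96). Pool over visits, with attended patient-visits as the denominator.

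Show the same common-window figures beside the 2% table. Footnote all by-arm TEAE tables to say that scheduled contact was weekly in treated boys and up to 24 weeks apart in controls. Keep the full TEAE and SAE tables as planned.

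**Cost.** SAP wording and one derived table from AE onset dates and visit dates; no visit or clinical procedure changes. The table uses about one-third of AE time and will be imprecise with few controls. It leaves some bias, because treated boys are still asked weekly within each window: residual ratios are about 1.27, 1.13 and 1.09 at half-lives of 4, 8 and 12 weeks. That limit should be stated with the table.
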